site as an unscheduled study visit for additional safety visits if the investigator feels necessary. All subjects will be assigned to a care level based on the assessment as described in Section 5.3.1.1 (Subject Care Plan Model). Sites should ensure that subjects adhere to the study visits listed in Table 7. Subjects who cannot complete their study visit per the visit schedule should ensure they do not run out of study drug prior to their next study visit. Compliance is critical to ensure adequate drug exposure.

Some of the Treatment Period study visits and visit activities (including but not limited to vital signs, clinical laboratory tests, and concomitant medication assessment) may be conducted in the home or non-hospital/clinic environment by qualified individuals at the request of the Investigator, with approval from the Sponsor, and with the agreement of the subject.

Virologic failure criteria will be evaluated and applied by the Investigator as detailed in Section 5.4.3.

Subjects who prematurely discontinue from the Treatment Period should return for a Treatment Discontinuation Visit and undergo the study procedures as outlined in Table 7 and as described in Section 5.3.1.1. Ideally, this should occur on the day of study drug discontinuation, but is recommended to be no later than 2 days after their final dose of study drug and prior to the initiation of any other anti-HCV therapy if applicable. Following completion or premature discontinuation of study drug treatment, all subjects will enter the 260-week Post-Treatment Period.

The Treatment Period will assess safety, antiviral response, and clinical outcomes, including all-cause death, liver-related death, liver decompensation, occurrence of hepatocellular carcinoma, and liver transplantation.

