Moderate ascites = Ascites manifested by moderate symmetrical distension of the abdomen.

Severe ascites = Large or gross ascites with marked abdominal distension.

** Grade 0: normal consciousness, personality, neurological examination, electroencephalogram.

Grade 1: restless, sleep disturbed, irritable/agitated, tremor, impaired handwriting, 5 cps waves.

Grade 2: lethargic, time-disoriented, inappropriate behavior, asterixis, ataxia, slow triphasic waves.

Grade 3: somnolent, stuporous, place-disoriented, hyperactive reflexes, rigidity, slower waves.

Grade 4: unarousable coma, no personality/behavior, decerebrate, slow 2 to 3 cps delta activity.

Clinical Assessment of Liver Decompensation

A clinical assessment of hepatic encephalopathy and ascites will be performed at Study Day 1 prior to dosing to confirm the subject has not progressed to hepatic decompensation since screening for all subjects who have compensated cirrhosis. Grading system guidelines for ascites are listed above in [Table 9](#).

Hepatocellular Carcinoma Screening: Liver Ultrasound

In order to monitor for the presence of hepatocellular carcinoma (HCC), an ultrasound of the liver will be performed as indicated in [Table 7](#).

For subjects with compensated cirrhosis:

- Subjects receiving 12 weeks of treatment will have a liver ultrasound performed at the screening visit and all Post-Treatment visits except Post-Treatment Week 4
- Subjects receiving 24 weeks of treatment will have a liver ultrasound performed at the screening visit, Week 24 visit, and all Post-Treatment visits except the Post-Treatment Week 4 and Post-Treatment Week 12.

For subjects without cirrhosis: Liver ultrasound will be performed at the Screening Visit, Post-Treatment Week 52, Post-Treatment Week 156 and Post-Treatment Week 260.

Subjects with a historical negative liver ultrasound, CT or MRI (within 3 months prior to screening) are not required to undergo a screening ultrasound.

A positive Ultrasound result suspicious for HCC during the treatment or post-treatment period will be confirmed with CT scan or MRI.

Assessment of Clinical Outcomes

The following clinical outcomes will be assessed during the study at visits outlined in **Table 7:**

- All-cause death: Death due to any cause.
- Liver-related death: Death as the result of a liver-related cause, based on the opinion of the clinical site principal investigator.
- Liver transplantation: Any subject who had undergone liver transplantation.

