- Liver decompensation: Development of any of the following conditions: ascites, hepatic encephalopathy, or variceal bleeding.
- Hepatocellular carcinoma (HCC): Any subject in whom, at any time during the study, HCC developed. HCC is defined by histologic confirmation or a > 1 cm mass lesion on cross-sectional imaging that meets the diagnostic criteria of HCC according to AASLD guidelines.³⁰

- Composite of any of the above outcomes.

Clinical Outcome events that occur during the Treatment Period through Post-Treatment Week 4 are to be recorded and documented in the AE/SAE eCRF (Section [6.0](#)) in addition to being captured in the Clinical Outcome eCRF. Clinical Outcome events that occur after Post-Treatment Week 4 are to be recorded in the Clinical Outcome eCRFs only, except when the clinical outcome is death, in which case the SAE eCRF would also need to be completed.

An independent outcome committee will review and adjudicate the validity of each clinical outcome as per the charter.

HCV Resistance Testing Plasma Sample

A plasma sample for HCV resistance testing will be collected at the study visits, indicated in [Table 7](#). Specific instructions for preparation and storage of the samples will be provided by the central laboratory, the Sponsor, or its designee.

Subject Care Plan Model

The Subject Care Plan model is a mechanism that allows subjects to receive reminders for upcoming study visits, reminders to take study drugs, information about their HCV RNA values (if applicable) and/or receive disease specific education and encouragement at varying frequencies of contact.

Subjects will be contacted by a designated nurse educator, contracted by the sponsor, throughout the trial. The nurse educator may interact with subjects by phone, email, in-person visit, postal mail, text message or combinations of these listed communications to facilitate the assigned subject care plan level.

The investigator or his/her designated site personnel will register each subject in the web-based care model portal after enrollment. However, if the web-based portal is not operable, or the site information is not available in the portal, the nurse educator may obtain this information verbally from the site. The subject profile form will collect broad

demographic information, including but not limited to, the subject's contact information and best time of contact.

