5.5.5 Blinding

This is an open-label study.

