6.1 Definitions**6.1.1 Adverse Event**

An adverse event (AE) is defined as any untoward medical occurrence in a patient or clinical investigation subject administered a pharmaceutical product and which does not necessarily have a causal relationship with this treatment. An adverse event can therefore

be any unfavorable and unintended sign (including an abnormal laboratory finding), symptom, or disease temporally associated with the use of a medicinal (investigational) product, whether or not the event is considered causally related to the use of the product.

Such an event can result from use of the drug as stipulated in the protocol or labeling, as well as from accidental or intentional overdose, drug abuse, or drug withdrawal. Any worsening of a pre-existing condition or illness is considered an adverse event.

Worsening in severity of a reported adverse event should be reported as a new adverse event. Laboratory abnormalities and changes in vital signs are considered to be adverse events only if they result in discontinuation from the study, necessitate therapeutic medical intervention, [meets protocol specific criteria (see Section 6.7 regarding toxicity management)] and/or if the investigator considers them to be adverse events.

An elective surgery/procedure scheduled to occur during a study will not be considered an adverse event if the surgery/procedure is being performed for a pre-existing condition or the surgery/procedure has been pre-planned prior to study entry. However, if the pre-existing condition deteriorates unexpectedly during the study (e.g., surgery performed earlier than planned), then the deterioration of the condition for which the elective surgery/procedure is being done will be considered an adverse event.

Protocol-defined clinical outcomes consist of:

- All-cause death: Death due to any cause.
- Liver-related death: Death as the result of a liver-related cause, based on the opinion of the clinical site principal investigator.
- Liver transplantation: Any subject who had undergone liver transplantation
- Liver decompensation: Development of any of the following conditions: ascites, hepatic encephalopathy, or variceal bleeding.
- Hepatocellular carcinoma (HCC): Any subject in whom, at any time during the study, HCC developed. HCC is defined by histologic confirmation or a ≥ 1 cm mass lesion on cross-sectional imaging meets the diagnostic criteria of HCC according to AASLD guidelines.³⁰

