10.0 Efficacy Analysis

10.1 General Considerations

The primary efficacy analysis on clinical outcomes will be performed on all subjects in the ITT population as defined in Section 5.1. All other efficacy analyses will be performed on the ITT-II population.

Treatment effects will be evaluated based on a two-sided significance level of 0.05 (when rounded to three decimal places). The data from the ITT-II population will be presented in one column/row as it represents the labelled treatment.

Plasma HCV RNA levels will be determined for each sample collected by the central laboratory using the COBAS[®] AmpliPrep/COBAS[®] TaqMan[®] HCV Test, v2.0. The lower limit of quantification (LLOQ) and the lower limit of detection (LLOD) is 15 IU/mL. HCV RNA results that are detectable but not quantifiable are reported as "< 15 IU/mL" and results that are not detectable are reported as "-NON-DETECTED."

Assessment of Clinical Outcomes

Incidence of the following clinical outcome events will be collected during the 12/24 weeks of treatment and the 5-year (PT Week 260) Post-Treatment Period. The data reported on the "Clinical Outcome" eCRFs will be adjudicated by an independent outcome committee and results of the adjudication will be added to the "Clinical Outcome" eCRFs:

- All-cause death: Death due to any cause.
- Liver-related death: Death as the result of a liver-related cause.
- Liver decompensation: Development of any of the following conditions: ascites, hepatic encephalopathy, or variceal bleeding.

- Liver transplantation: any subject who had a liver transplantation
- Hepatocellular carcinoma (HCC): development of HCC in any subject at any time during the study. HCC is defined by histologic confirmation or a > 1 cm mass lesion on cross-sectional imaging that meets the diagnostic criteria for HCC according to EASL guidelines.
- Composite of any of the above outcomes.

Definitions for HCV RNA Efficacy Endpoints

Note that a confirmed quantifiable post-treatment value is defined as two consecutive post-treatment HCV RNA measurements \geq LLOQ. During treatment, a confirmed quantifiable value is defined as any two consecutive HCV RNA values \geq LLOQ, either both during treatment or at the final treatment measurement and the next consecutive post-treatment measurement.

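### Liver-related death is assigned by site investigators likely to know SVR12 status, and the plan does not say whose classification is analysed or whether the committee is masked

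*Protocol*

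**What the plan says.** Liver-related death is one of the six events in the primary analysis, which compares subjects who achieve SVR12 with those who do not (Protocol 8.1.2.1, SAP 10.3).

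Protocol 5.3.1.1 defines it as "Death as the result of a liver-related cause, based on the opinion of the clinical site principal investigator", and the adverse-event definitions in 6.1.1 repeat the phrase "based on the opinion of the clinical site principal investigator". The same part of 5.3.1.1 adds: "An independent outcome committee will review and adjudicate the validity of each clinical outcome as per the charter".

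SAP 10.1 words the event differently: "Liver-related death: Death as the result of a liver-related cause", with nobody named as deciding the cause. It says that the reported outcome data "will be adjudicated by an independent outcome committee and results of the adjudication will be added to the" Clinical Outcome eCRFs.

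SAP 10.3 then analyses time to an event of interest, without saying whether this means the reported or the adjudicated event. It makes all-cause death a censoring event for liver-related death. SAP 10.2 makes no multiplicity adjustment.

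On masking, Protocol 5.5.5 says only: "This is an open-label study".

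**The concern.** The exposure in the primary comparison is a virologic result, and the person whose opinion defines the event is likely to know it. During treatment, "Virologic failure criteria will be evaluated and applied by the Investigator" (Protocol 5.1.2). HCV RNA is sampled at every post-treatment visit (Table 7). Questionnaires must be completed before HCV RNA results are reviewed at the visit (5.3.1.1), so such review is expected. Sites also record anti-HCV medication after treatment (5.2.3). No sentence says outright that the investigator sees the post-treatment results, which come from a central laboratory, but nothing withholds them.

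A physician who knows that treatment failed may lean towards a hepatic cause of death, and one who knows that it succeeded may lean away. Because a death not called liver-related is censored for this event, attribution alone decides between event and censoring. Such an error would differ between the groups and favour the hypothesis. The expected number of non-SVR12 deaths is small, so little reclassification is needed to move the estimate. With no multiplicity adjustment, a result for liver-related death could be reported on its own at the 0.05 level.

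**Working it through.** **The plan's power figure.** Protocol 8.2 claims more than 80% power for the composite. The inputs are 2,000 subjects, 4% without SVR12 (80 against 1,920), a 20% five-year rate in that group, hazard ratio 0.25, dropout up to 20% and two-sided α of 0.05. I take dropout as exponential, reaching 20% at five years (an assumption).

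- Non-SVR12 events: 80 × 0.5 × (1 − 0.8²) = 80 × 0.18 = 14.4.
- SVR12 events: 1,920 × (0.25/1.25) × (1 − 0.8^1.25) = 1,920 × 0.0487 = 93.5.
- Total: 107.9.
- Schoenfeld power: Φ(|ln 0.25| × √(0.04 × 0.96 × 107.9) − 1.960) = Φ(0.862) = 80.6%.

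This agrees with the stated figure. The composite counts every death whatever its cause, so cause attribution does not enter it.

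**Who decides the event.**

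| Question | Protocol 5.3.1.1 and 6.1.1 | SAP 10.1 and 10.3 |
|---|---|---|
| Who attributes the cause? | Site principal investigator | Not named |
| What does the committee do? | Adjudicates validity, under a charter | Adjudicates; results added to the eCRF |
| Which classification is analysed? | Not stated | Not stated |
| What if the two disagree? | Not stated | Not stated |
| Is the committee masked to SVR12? | Not stated | Not stated |

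**Illustration of size.** Planned enrolment is 1,650 + 600 = 2,250 (SAP 4.3), so 4% gives 90 non-SVR12 and 2,160 SVR12 subjects. Protocol 3.0 gives five-year mortality in genotype 1 patients of 14.4% without SVR and 6.7% with SVR. The 30% liver share and the shifts are assumptions; the documents give neither.

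- Deaths: 90 × 14.4% = 13.0 and 2,160 × 6.7% = 144.7.
- Liver-related at 30%: 3.9 and 43.4.
- Risk ratio, non-SVR12 to SVR12, with equal shares: 14.4/6.7 = 2.15.

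| Share called liver-related (non-SVR12 / SVR12) | Apparent risk ratio | Non-SVR12 deaths moved | SVR12 deaths moved |
|---|---|---|---|
| 30% / 30% | 2.15 | 0 | 0 |
| 35% / 25% | 2.15 × 35/25 = 3.0 | 13.0 × 5% = 0.65 | 144.7 × 5% = 7.2 |
| 40% / 20% | 2.15 × 40/20 = 4.3 | 13.0 × 10% = 1.3 | 144.7 × 10% = 14.5 |
| 35% / 30% | 2.15 × 35/30 = 2.5 | 0.65 | 0 |
| 40% / 30% | 2.15 × 40/30 = 2.9 | 1.3 | 0 |

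The larger ratios therefore need about 7 to 14 SVR12 deaths moved out of the liver category as well as about one non-SVR12 death moved in.

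**False positives.** Log-rank simulations (4,000 runs, 2,000 subjects of whom 80 non-SVR12, the same dropout) assumed no true SVR12 effect on death, with five-year mortality of 6.7% or 14.4% in both groups.

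| Share called liver-related (non-SVR12 / SVR12) | Rejection rate at 0.05 |
|---|---|
| 30% / 30% | 4.2–4.5% |
| 45% / 30% | 14–19% |
| 60% / 30% | 27–39% |
| All-cause death, same null | 4.7–5.0% |

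These rates show sensitivity to assumed shares. They do not estimate the bias in this trial.

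**The case against.** The strongest reply is that the process is already sound: the investigator reports, the committee adjudicates, and the adjudicated data are analysed. All-cause death is itself a listed outcome, so every death should reach the committee. In SAP 10.1 the adjudication sentence introduces the event definitions, and the SAP drops the reference to the investigator's opinion. The Protocol wording could then be read as a reporting definition for sites, and the charter may settle both masking and precedence.

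Much of this stands. A reader might infer that the analysed event is simply whatever an unmasked investigator called it, or that the committee is known to be unmasked. The documents support neither: independent adjudication is planned, and the charter has not been seen. What remains is that the Protocol twice makes the investigator's opinion part of a primary event definition, the SAP words the event differently, and SAP 10.3 does not say which classification is used.

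It is also fair that an equal true liver share is only a convenience. Protocol 3.0 cites studies reporting lower liver-related mortality after SVR, so a higher liver share among non-responders' deaths could be real. The illustration cannot separate that from biased attribution; masked classification would protect against the bias.

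The reach is limited. Deaths enter all-cause death and the composite regardless of cause, and the sample size rests on the composite. Ascites and encephalopathy also involve judgement and do enter the composite, but I have not quantified any effect there.

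**Conclusion.** The point holds as a conflict between the documents plus an unspecified analysis rule, and is a cheap improvement. The Protocol and SAP differ on who attributes liver-related death, the analysed classification is not named, and masking of the committee is not stated. If attribution followed known SVR12 status, this one analysis would be biased towards the hypothesis. Under the assumed 30% share and shifts of 5 to 10 points, the risk ratio rises from 2.15 to 3.0–4.3 when both groups shift, or 2.5–2.9 when only the non-SVR12 deaths do.

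It would go too far to say that the plan will produce a spurious SVR12 effect, or that one or two non-SVR12 deaths explain the larger ratios. The first depends on conduct and a charter that cannot be checked here; the second is contradicted by the arithmetic. All-cause death, the composite's death component and the stated power are unchanged.

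**What to change.** - **Protocol 5.3.1.1 and 6.1.1:** define liver-related death as classified by the existing independent outcome committee, from event packages that omit HCV RNA results, SVR12 status and post-treatment anti-HCV therapy.
- **SAP 10.1 and 10.3:** state that the committee's classification is the analysed event and settles any disagreement, with the investigator's classification as a sensitivity analysis.
- **Charter:** align it with this wording, or, if it already provides for masking and precedence, carry those provisions into the Protocol and SAP.

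The cost is wording and some redaction of packages for a committee that already exists. Masking may be imperfect, because some clinical records will still reveal virologic status. No visit, sample size or clinical procedure changes.

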5.3.1.2 Blood Samples for Pharmacogenetic Analysis

IL28B Sample

One (required) 4mL whole blood sample for deoxyribonucleic acid (DNA) isolation will be collected from each subject at screening for Interleukin 28B (IL28B) pharmacogenetic analysis and related markers. If the sample is not collected at this visit, it may be collected at any time throughout the study. This sample will not be used for any testing other than IL28B genotypes.

Specific instructions for sample collection and storage will be provided by the central laboratory, the Sponsor, or its designee. Samples will be used only for IL-28B testing and then destroyed.

5.3.1.3 Meals and Dietary Requirement

All study drugs should be dosed together and administered with food, i.e., the morning dose of ABT-450/r/ABT-267, ABT-333 and RBV(if applicable) should be taken together with food and the evening dose of ABT-333 and RBV (if applicable) should be taken together with food.

5.3.2 Efficacy Variables**5.3.2.1 Primary Variable**

The primary endpoint is the incidence of all-cause death, liver-related death, liver decompensation, liver transplantation, hepatocellular carcinoma, and the composite of any of the above outcomes observed during the post-treatment period.

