Study Drug	ABT-450/ritonavir/ABT-267, ABT-333, ribavirin
Day 1	First day a subject took study drug
Treatment Period	Baseline/Day 1 through the last dose of study drug
Post-Treatment Period	Day after the last dose of study drug through Post-Treatment Week 260 or Post-Treatment Discontinuation

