8.1.2 Efficacy

The primary efficacy analysis on clinical outcomes will be performed on all subjects in the ITT population. All other efficacy analyses will be performed on the ITT-II population.

Plasma HCV RNA levels will be determined for each sample collected by the central laboratory using the COBAS® AmpliPrep HCV assay version 2.0. For this assay, the lower limit of quantification (LLOQ) is 15 IU/mL.

Incidence of all-cause death, liver-related death, liver decompensation, liver transplantation, and hepatocellular carcinoma as defined in protocol Section 5.3.1.1 will be collected during the 5-year (PT Week 260) Post-Treatment Period.

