10.3 Primary Efficacy Analysis

The primary efficacy analysis will be conducted among subjects in the ITT population as described in Section 5.1. HCV RNA values and SVR₁₂ will be imputed as described in Section 6.3.

The primary efficacy endpoint is to assess the effect of response to treatment (as assessed by SVR₁₂ status) on clinical outcomes by comparing the time to incidence of the following events between subjects who achieve SVR₁₂ and those who do not.

- All-cause death
- Liver-related death
- Liver decompensation
- Liver transplantation
- Hepatocellular carcinoma

- Composite of any of the above outcomes

For each of the six event types as listed above, a subject's time to event will be defined as the number of days from the first day of study drug dosing for the subject to the day the subject experiences an event of interest. All events of interest will be included, regardless of whether the event occurred while the subject is still taking study drug or has previously discontinued study drug. If the subject does not experience an event of interest nor has the subject died (all-cause death), the subject's data will be censored at the date of the subject's last available assessment of clinical outcomes. For subjects with no post-baseline assessment, the subject's data will be censored on the first day of study drug dosing. All-cause death is a censoring event for liver-related death, liver decompensation, liver transplantation and hepatocellular carcinoma. Time to the composite of clinical outcomes is the time to the first occurrence of any clinical outcome.

For each of the six event types, the distribution of time to event will be estimated for subjects who have achieved SVR₁₂ and those who haven't using Kaplan-Meier methodology and compared between the subjects who have achieved SVR₁₂ and those who haven't using the log-rank test.

For each of the six event types, the 1-, 2-, 3-, 4-, and 5-year event-free survival rate will be estimated using Kaplan-Meier methodology and a 95% confidence interval will be constructed separately for those who have achieved SVR₁₂ and those who have not. For each of the six event types, a Cox proportional hazards (PH) model will be constructed to include all the baseline characteristics as described in Section 7.1, SVR₁₂ status, and other variables as appropriate.

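### Primary event window and time origin are contradictory: Protocol 5.3.2.1 counts post-treatment events, SAP 10.3 counts all events from first dose, and the protocol itself is mixed

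*Protocol*

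**What the plan says.** **Post-treatment only.** Protocol 5.3.2.1, which defines the primary variable, ends with "the composite of any of the above outcomes observed during the post-treatment period". Protocol 8.1.2 names each component and says its incidence "will be collected during the 5-year (PT Week 260) Post-Treatment Period". Protocol 1.3 defines the period as "Day after the last dose of study drug through Post-Treatment Week 260 or Post-Treatment Discontinuation".

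**From first dose.** SAP 10.1 says the same events "will be collected during the 12/24 weeks of treatment and the 5-year (PT Week 260) Post-Treatment Period". SAP 10.3 gives this rule for time to event: "number of days from the first day of study drug dosing for the subject to the day the subject experiences an event of interest". It adds: "All events of interest will be included, regardless of whether the event occurred while the subject is still taking study drug".

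**Protocol text on the SAP's side.** Protocol 5.1.2 states: "The Treatment Period will assess safety, antiviral response, and clinical outcomes". The synopsis (criteria for evaluation) also places outcome assessment both on and after treatment. Protocol 5.3.1.1 defines HCC as arising at any point in the study. Protocol 6.1.1 describes recording of outcome events both on treatment and later, then says these outcomes are part of the study endpoints.

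**Silent.** Protocol 8.1.2.1 specifies the Cox comparison but gives neither an event window nor a time origin.

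**The concern.** The primary objective is the effect of SVR12 status on later liver disease. SVR12 is determined 12 weeks after the last dose. A decompensation, HCC or transplant during treatment comes before that status and cannot result from it. The causal arrow can run the other way: the event may stop treatment, and SAP 10.1 lists premature discontinuation without virologic failure as a category of SVR12 non-response. A subject who dies on treatment has no post-treatment HCV RNA and is imputed as a failure under SAP 6.3. Events of both kinds would count towards an apparent benefit of SVR12.

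The time origin matters as well. Treating five years as 260 weeks, the SAP's 5-year event-free rate from first dose ends at post-treatment week 260 − 12 = 248 for a 12-week subject and 260 − 24 = 236 for a 24-week subject. Neither is the 260-week post-treatment incidence of Protocol 5.3.2.1, and the gap differs by regimen.

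**Working it through.** **Inputs** (Protocol 8.2, SAP 4.3): 4% without SVR12; 20% composite event rate at 5 years in that group; hazard ratio 0.25; at least 2,000 subjects (planned 1,650 + 600 = 2,250); dropout up to 20%; two-sided alpha 0.05.

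**Assumptions:** constant hazards from first dose, and 20% exponential dropout over 5 years.

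**Hazards per year:** non-SVR12, −ln(0.8)/5 = 0.0446; SVR12, 0.25 × 0.0446 = 0.0112; dropout, −ln(0.8)/5 = 0.0446.

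**Expected events in a group of n over T years:** n × λ/(λ + λd) × [1 − exp(−(λ + λd)T)].

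**Step 1. Reproduce the plan's power.** With N = 2,000 and T = 5:
- Non-SVR12: 80 × 0.5 × (1 − e^(−0.446)) = 14.4.
- SVR12: 1,920 × 0.2 × (1 − e^(−0.279)) = 93.5.
- Total 107.9 events. Schoenfeld power = Φ(√(107.9 × 0.04 × 0.96) × ln 4 − 1.96) = 0.806; 107 events are needed for 80%.
- Without dropout: 120.2 events, power 0.846.
- A simulated log-rank test gives 0.977 with dropout and 0.985 without.

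The stated figure of more than 80% reproduces. Only the harsher reading, which multiplies N by 0.8, falls short at 2,000 (0.759); it gives 0.807 at 2,250.

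**Step 2. Size of the treatment period** (N = 2,000, 20% dropout). For 12 weeks, T = 12/52 = 0.231: 40 × (1 − e^(−0.0206)) = 0.82 non-SVR12 events, and 384 × (1 − e^(−0.0129)) = 4.91 SVR12 events.

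| Regimen assumed for all | On-treatment events | All events from first dose | Share | Power with / without on-treatment events |
|---|---|---|---|---|
| 12 weeks | 0.82 + 4.91 = 5.7 | 112.1 | 5.1% | 0.820 / 0.800 |
| 24 weeks | 1.61 + 9.76 = 11.4 | 116.3 | 9.8% | 0.834 / 0.795 |

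The second row is a ceiling that cannot occur in this study. Only cirrhotic subjects with GT1a, unknown or mixed subtype are assigned 24 weeks, and F4 enrolment is capped at 150 of about 600. If a quarter of all subjects had 24 weeks (150/600, assumed to hold in TOPAZ-I too, with equal hazards), the figure is 0.75 × 5.7 + 0.25 × 11.4 = 7.1 of 0.75 × 112.1 + 0.25 × 116.3 = 113.2, or 6.3%.

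**Step 3. Sensitivity of the small group.** At N = 2,250 the same formula gives 16.2 non-SVR12 and 105.2 SVR12 events. Suppose k further on-treatment events occur in subjects who then become non-SVR12. The documents give no value for k. The hazard ratio becomes 0.25 × 16.2/(16.2 + k): 0.235, 0.222 and 0.211 for k = 1, 2 and 3.

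The standard error of the log hazard ratio is √(1/16.2 + 1/105.2) = 0.267, so the 95% interval around 0.25 is about 0.15 to 0.42. The shift is ln(17.2/16.2)/0.267 = 0.22 standard errors for k = 1 and ln(19.2/16.2)/0.267 = 0.64 for k = 3.

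**The case against.** The strongest reply is that the SAP settles the matter. SAP 4.4 says analyses follow the methods in the SAP, SAP 10.3 is unambiguous, and much of the protocol expects outcomes to be captured on treatment. On this view 5.3.2.1 is a loosely worded line. Protocol 8.1.2 says where incidence is collected but does not say only there; read as a strict limit it would contradict Table 7 and 5.3.1.1.

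Much of this stands:
- A reader might infer that the SAP overrides a clear protocol rule. The documents do not support that, because the protocol points both ways.
- A reader might expect two analysts to report different results. In practice the SAP would be followed, and its result is predictable.
- A reader might infer a materially biased hazard ratio. The k events are assumed, and their effect is a fraction of a standard error. Constant hazard from Day 1 may also overstate early events generally, since Protocol 5.2.2 excludes prior decompensation, Child-Pugh B or C, and confirmed HCC.

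What does not fall is the contradiction itself. The section that defines the primary variable names one window, the primary analysis uses another, and no text reconciles them or presents the SAP rule as a deliberate change. Assessing an outcome on treatment is not the same as counting it in the primary endpoint.

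A further fair objection is that cutting at last dose does not remove the causal problem, because events in post-treatment weeks 1 to 12 also precede SVR12. That is correct. It is a separate issue of grouping by a post-baseline status.

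**Conclusion.** The point holds as a contradiction over the primary event set and its time origin, within the protocol and between it and the SAP. It is more than a clerical slip, because it decides which events enter the primary comparison and when the clock starts.

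The expected numerical effect is small: about 6 of 112 composite events (5.1%) with everyone on 12 weeks, N = 2,000, constant hazards and 20% dropout, with Schoenfeld power 0.820 against 0.800. The average calculation does not capture events that themselves lead to non-SVR12. Those would fall on a group with only about 14 to 16 expected events, but their number is unknown, so no bias of a given size can be claimed. The planned power is not undermined. The change is worth making because it is cheap and concerns the primary endpoint.

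**What to change.** State one event window and one matching time origin in Protocol 5.3.2.1, 8.1.2 and 8.1.2.1 and in SAP 10.1 and 10.3. The version consistent with Protocol 5.3.2.1 and the objective is:

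- Start the clock on the day after last dose and count first events from then on.
- Treat a subject who dies on treatment as not at risk. Treat a subject whose first event of a given type occurs on treatment as not at risk for that type or for the composite.
- List treatment-period events, including deaths, separately by type.
- Keep the SAP's analysis of all events from first dose, in the full ITT population, as a named sensitivity analysis.

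The origin must move with the window. Dropping on-treatment events while keeping first dose as the origin would give every retained subject 12 or 24 weeks of guaranteed event-free time, of different length by regimen. Amending the protocol to adopt the SAP's window would also end the contradiction, but it fits the objective less well.

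**Cost:** wording and derivation only, since outcomes on treatment are already recorded on the Clinical Outcome eCRF. About 5% fewer primary events are expected, and a few subjects fall outside the primary risk set, which should be reported against the ITT population. Events in post-treatment weeks 1 to 12 need their own solution.
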